## Appendix A: Study Protocol

### Transitioning Youth Out of Homelessness 2.5: A Co-Designed Strengths-Based Leadership Program for Young People Transitioning Out of Homelessness

#### Abstract

**Background:** This project builds on our current community-based randomized clinical trial (Transitioning Youth Out of Homelessness 2.0) utilizing coaching and a co-designed leadership guide to target identity capital (purpose, control, self-efficacy, and self-esteem) for youth transitioning out of homelessness (all participants are also receiving rent subsidies). Based on preliminary feedback from study youth and coaches involved in the intervention arm, we plan to modify the leadership guide and pilot it in the form of an in-person, four-week leadership program (vs. independent learning in our current study).

**Objectives:** The overarching objective of this mixed methods pilot project is to co-develop and test a strengths-based leadership program targeting identity capital for youth (16 – 24 years of age) transitioning out of homelessness. Specifically, the objectives are to:

1. Modify the leadership guide being used in our current study so it can be delivered as an in-person leadership program.
2. Co-develop and pilot a four-week, strengths-based leadership program for young people transitioning out of homelessness.
3. Determine the feasibility and acceptability of the leadership guide when delivered as a four-week, in-person program (as opposed to independent learning in our current study).
4. Examine whether self-reported measures of identity capital and knowledge of program material show improvement immediately post-program compared to baseline.
5. Explore whether there are differences in outcomes by sub-groups (e.g., gender, age, identification as 2SLGBTQ+, child welfare involvement) and/or program participation levels.

**Methods:** This study will employ a mixed method design embedded within a Community Based Participatory Action Research framework. *Phase One (Objectives 1 & 2):* An established team of

two coaches and four youth lived expert advisors will collaborate with a Toronto-based high school teacher on modifying the guide and co-developing the leadership program. *Phase Two (Objective 2)*: Participants (n = 30) will be recruited from our community partner agencies. Two four-week leadership programs (15 youth per program) will be led by coaches from our current study with our youth advisors participating as paid leadership interns. Data collection will occur at baseline (baseline demographic questionnaire; identity capital questionnaire; knowledge assessment questionnaire) and immediately post-program (identity capital questionnaire; knowledge assessment questionnaire; program feedback questionnaire; focus group). We will also track program session attendance. *Phase Three (Objectives 3, 4 & 5)*: Quantitative questionnaires and program attendance will be examined using descriptive statistics and non-parametric or t-tests and Cohen's d effect size. Qualitative focus groups (primarily centred around acceptability) will be explored using reflexive thematic analysis with a critical social theoretical lens.

**Significance:** If this modified delivery of the leadership guide shows promise, we plan to incorporate it into a national scale-up alongside rent subsidies and coaching.

## 1. Background and Rationale

Drivers into youth homelessness are well documented and include multiple adverse childhood experiences, poverty, discrimination, and child welfare involvement (Abramovich, 2016; Centrepoint, 2022; Crandall et al., 2019; Dej, 2020; Gaetz et al., 2016; Karabanow, 2004; Karabanow et al., 2016; Liu et al., 2021; Morton et al., 2018; Samuels et al., 2019). The impact of being failed by people and systems intended to nurture and support have profound impacts on the health and well-being of these inequitably served youth (Abramovich, 2016; Bonakdar et al., 2023; Brueckner et al., 2011; Crandall et al., 2019; Dej, 2020; Gaetz et al., 2016; Karabanow et al., 2016; Kidd et al., 2016; Kidd et al., 2021; Kozloff et al., 2016; Liu et al., 2021; Mayock et al., 2011; Samuels et al., 2019; Thulien et al., 2018). For example, a 2019 pan-Canadian survey of 1,375 young people accessing supports within the youth homelessness system (e.g., shelter drop-in services) reported 74% of youth were experiencing high degrees of mental health distress (e.g., anxiety and/or depression) and 35% had tried to commit suicide at least once (Kidd et al., 2021). Levels of mental health distress and suicidality were the highest among younger

respondents, those with an earlier age of first homelessness, and those who identified as a woman/girl, Indigenous, and/or two-spirit, lesbian, gay, bisexual, transgender, or queer (2SLGBTQ+; Kidd et al., 2021). A notable 61% reported involvement with child protective services, with just under half (48%) reporting that they did not receive any help regarding a suitable plan for where they could go or how they could support themselves after exiting the child welfare system (Bonakdar et al., 2023).

The problem of no suitable plan for long-term, equitable social and economic inclusion (i.e., supports beyond housing and welfare payments) is emerging as a critical societal issue for young people attempting to transition away from homelessness. Research from the small but growing body of longitudinal studies on post-homelessness experiences highlights that, despite the attainment of relative housing stability and irrespective of the type of housing acquired (market rent with limited or no social service supports vs. subsidized with social services supports), too many youth are surviving, not thriving – struggling with poverty-level incomes, feelings of purposelessness, loneliness, “outsiderness”, meaninglessness, hopelessness, and a sense of being stuck (Brueckner et al., 2011; Karabanow et al., 2016; Kidd et al., 2016; Kozloff et al., 2016; Mayock et al., 2011; Thulien et al., 2018, p. 6). Moreover, there is an extremely limited evidence base regarding effective and rigorous interventions for this population (Morton et al., 2020), especially when it comes to inclusion health – an emergent approach that aims to address extreme health and social inequities (Luchenski et al., 2018).

This project builds on our 2.5-year community-based pilot mixed method randomized clinical trial of rent subsidies and mentorship for youth exiting homelessness (Transitioning Youth Out of Homelessness 1.0; Thulien et al., 2019). While we were unable to prove that youth receiving rent subsidies and mentorship had significantly better socioeconomic inclusion outcomes compared to the group who received rent subsidies only, there were signals from our quantitative and qualitative data that connecting with informal mentors – people outside the study who played “coach-like” roles (e.g., asking powerful, future-oriented questions vs. simply providing advice) – was key to fostering socioeconomic inclusion (proxy indicators of socioeconomic inclusion encompassed measures such as community integration, self-esteem, and engagement in education, employment, and training; Thulien et al., 2022; Thulien et al., 2023).

Drawing on 71 in-depth interviews conducted by [name] over the 2.5-year study period, the study also highlighted the crucial role of identity capital – a sense of purpose, control, self-efficacy, and self-esteem – as an important mediator of socioeconomic inclusion (Thulien et al., 2023). When people with limited identity capital encounter challenges, they are more likely to give up and take the path of least resistance (Côté, 2016). For study participants, this inequitable fostering of identity capital meant living in the legacy of their past (e.g., a sense of powerlessness over their futures) and becoming trapped in the “fog” of exclusion (Thulien et al., 2023, p. 5).

Building on these findings, our team of youth with lived expertise, community partners, and researchers, developed Transitioning Youth Out of Homelessness (TYOH) 2.0 – a pilot mixed method randomized clinical trial of rent subsidies and coaching along with a co-designed leadership guide for youth exiting homelessness (ClinicalTrials.gov, 2023). Briefly, all participants ( $n = 40$ ) receive rent subsidies and half are randomly assigned a solution-focused coach and a leadership guide which was co-designed with youth who have experienced homelessness (including several youth from the TYOH 1.0 study). Young people in the intervention group are expected to engage one-on-one with their coach, and independently with the leadership guide for one year. We are trying to understand if this more deliberate targeting of identity capital (alongside rent subsidies) will show promise as a way to improve socioeconomic inclusion outcomes. Our goal is to use these findings to conduct a larger national study.

Preliminary qualitative feedback from TYOH 2.0 coaches and study participants is that, while the co-designed leadership guide is a tremendous resource, it is hard for youth to independently engage with the material (e.g., showing up to one-on-one coaching sessions with minimal/no engagement with the leadership guide beforehand). We have also had enthusiastic feedback from teachers in the Ontario Education and Community Partnership Program (ECPP) – a program designed to reach youth not engaged in traditional school settings (e.g., shelter-based schools) – that the guide has tremendous potential for use in an ECPP setting (e.g., high school credits for guide completion). Given our plan to incorporate the leadership guide into a TYOH 2.0 national scale-up (alongside rent subsidies and coaching), we plan to collaborate with our established youth advisors on modifying the leadership guide and make it more engaging, align it with the

Ontario Ministry of Education core high school learning competencies, and pilot it in the form of an in-person, four-week leadership program with youth who are transitioning out of homelessness.

### **1.1. Objectives**

The overarching objective of this mixed methods pilot project is to co-develop and test a strengths-based leadership program targeting identity capital for youth (16 – 24 years old) transitioning out of homelessness. Specifically, the objectives are to:

1. Modify the leadership guide currently being used in TYOH 2.0 so it can be delivered as an in-person leadership program.
2. Co-develop and pilot a four-week, strengths-based leadership program for young people transitioning out of homelessness.
3. Determine the feasibility and acceptability of the leadership guide when delivered as a four-week, in-person program (as opposed to independent learning in the TYOH 2.0 study).
4. Examine whether self-reported measures of identity capital and knowledge of program material show improvement immediately post-program compared to baseline.
5. Explore whether there are differences in outcomes by sub-groups (e.g., gender, age, identification as 2SLGBTQ+, child welfare involvement) and/or program participation levels.

### **2. Methodology and Methods**

This study and the past five years of collaborative work in this area is grounded in a commitment to centring voices of youth with lived expertise as well as responding to priorities defined by community partners. The overall study draws on key principles of community-based participatory action research (CBPAR) and the qualitative component is framed with a critical social theoretical lens (Israel et al., 2018; Kirkham & Anderson, 2010; Moosa-Mitha, 2015; Strega, 2015):

- Research participants are viewed as experts in their own lives.

- Focus on highlighting how inequitable social structures of power – including the intersection of factors such as race, class, and gender – play out in the lives of participants.
- Search for examples of resilience and agency despite socio-structural inequities.
- Concerted effort to acknowledge and reduce power imbalances between researchers and the community.
- Equal value placed on academic knowledge and experiential knowledge.
- Commitment to co-producing practical, actionable data to build community capacity and improve the lives of research participants.
- Duty to remain invested with the community beyond the life of the research project.

## 2.1. Trial Design

This pilot study will employ a mixed methods design embedded within a CBPAR framework. The study will be conducted collaboratively with three long-term community partners who serve youth who are experiencing or have experienced homelessness: 1) Covenant House Toronto (Toronto, ON); 2) The RAFT (St. Catharines, ON); and 3) StepStones for Youth (Toronto, ON). We will prospectively register this trial on Clinicaltrials.gov once we receive Unity Health Toronto Research Ethics Board approval.

## 2.2. Eligibility Criteria

Eligible young people aged 16 – 24 years who have transitioned out of homelessness (e.g., no longer living in a shelter or couch surfing), defined as 3 consecutive months within the past 12 months, will be identified by our community partners (note: for the purpose of this study, youth living in foster care will be considered homeless). This age mandate was chosen because this is the age group served by our community partners. We have chosen to target the first year of exiting homelessness because our collective experience has shown that this can be a particularly precarious time for youth in terms of mental health challenges and risk of (re)experiencing homelessness (even if youth have attempted exits in the past).

In addition to the above age and housing **inclusion** criteria, study participants must:

- Be able to provide free and informed consent.

- Be able to understand English (leadership program and data collection will be conducted in English).
- Have experienced homelessness (e.g., unstable housing arrangements including shelter stays, foster care, and couch surfing) for 3 consecutive months in the past 12 months.
- Be able to consistently attend the four-week leadership program.

Young people will be **excluded** from the study if they are:

- Enrolled in a program or study with similar features to the TYOH 2.5 leadership program.

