## **2.7. Recruitment**

Study participants will be collaboratively recruited with our long-standing community partners: RAFT (St. Catharines); Covenant House (Toronto); StepStones for Youth (Toronto). RAFT and Covenant House work with young people who are experiencing or have experienced homelessness, and StepStones for Youth works with young people who are in or transitioning out of foster care. Youth will be invited to attend one of two four-week leadership programs – one in St. Catharines and one in Toronto.

Initial introduction to the study will be facilitated by our community partners, and interested participants directed to call or email the study research coordinator (Appendix C: Email and Phone Script). Community partners will utilize the study poster (Appendix D: Study Poster) and consent form (Appendix E: Consent Form) to help guide their initial discussions with potential participants. Screening for eligibility (Table 4) will be done over the phone or via a Zoom call by the research coordinator (Appendix F: Eligibility Screening Script). The eligibility screening checklist will be used verbally for all interested individuals. Notes will only be taken for the purpose of collecting broad, anonymous information about why a potential participant could not meet the eligibility criteria of being able to consistently attend the four-week leadership program, in order to inform our scale-up study (Appendix G: Screening Log). Our team will also record the number of young people deemed ineligible for the study.

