**Table 4. Eligibility Screening**

	Yes	No
16 – 24 years of age (at baseline)		
Have experienced homelessness (e.g., unstable housing arrangements including shelter stays, couch surfing, and foster care) for 3 consecutive months in the past 12 months		
Able to provide free and informed consent		
Able to speak and read English well enough to give consent and participate in the intervention and data collection		
Left homelessness within the past 12 months		
Be able to participate in the four-week, in-person leadership program (attend at least 6/8 sessions)		
NOT enrolled in a program or study with similar features to TYOH 2.5		
MUST SAY “YES” TO ALL TO BE ELIGIBLE FOR ENROLLMENT		

After eligibility screening, participants will be informed immediately over the phone whether they are eligible or ineligible for the study. If there is any confusion regarding eligibility and/or capacity to consent, the team member will reach out to [name] for guidance. In addition to being the study principal investigator, [name] is a nurse practitioner with over a decade of experience working exclusively with young people who are experiencing or have experienced homelessness.

Eligible participants will be provided the date/time/location of the first leadership program session. At the beginning of the first session, a research team member will carefully review the consent form with the participants to ensure they have a solid understanding of the study, with particular attention to: 1) overall study aim; 2) study length; 3) data collection; 4) data security; and 5) dissemination. A concerted effort has been made to ensure the consent form is in plain language. Highlighted throughout the document is the fact that informed consent is an ongoing process and can be negotiated at any time.

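### Does requiring three consecutive months of homelessness in the past twelve wrongly shut out youth who are 9 to 12 months past their exit?

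*Combined protocol and SAP*

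**What the plan says.** The combined protocol and SAP states the housing requirement in several places.

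- **Section 2.2, opening sentence.** Eligible youth have "transitioned out of homelessness (e.g., no longer living in a shelter or couch surfing), defined as 3 consecutive months" within a 12-month period. The same paragraph explains the target: "We have chosen to target the first year of exiting homelessness because our collective experience has shown" that this period is precarious.
- **Section 2.2, bullets.** These are introduced with "In addition to the above age and housing" criteria, and one of them is "Have experienced homelessness (e.g., unstable housing arrangements including shelter stays, foster care, and couch surfing) for 3 consecutive months in the past 12 months".
- **Table 4 (Section 2.7).** The three-in-twelve item appears again, with a separate row, "Left homelessness within the past 12 months". The answer must be yes "TO ALL TO BE ELIGIBLE FOR ENROLLMENT".
- **Section 2.6.** The recruitment description mentions homelessness in the past 12 months with no minimum duration.

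On handling and records, Section 2.7 says: "If there is any confusion regarding eligibility and/or capacity to consent, the team member will reach out to" the principal investigator. It also says "Notes will only be taken for the purpose of collecting broad, anonymous information about why a potential participant could not meet the eligibility criteria" on consistent attendance. Apart from that, it provides for a count of the young people found ineligible.

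**The concern.** A youth who has already left homelessness and must also show three months of it inside a 12-month look-back cannot have left very long ago. Taken literally, the rule admits only the first nine months after exit, although the stated rationale speaks of the first year. A second row allowing exits up to 12 months back then looks redundant, which suggests that the narrowing was not intended.

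Two further points add to the worry. The opening sentence of Section 2.2 can be parsed so that the three months describe time housed instead of time homeless. And if a coordinator turned someone away under the strict reading, the record described in Section 2.7 would show one more ineligible youth and no reason.

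At stake would be which population the report may describe, and how informative the recruitment and enrolment metrics are. Table 2 lists those metrics under the primary outcome.

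**Working it through.** The plan states no figure for the longest admissible time since exit, so there is none to reproduce. The check is calendar arithmetic on the criteria.

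**Inputs**

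- Look-back window: 12 months (Section 2.2 bullet; Table 4).
- Required spell: 3 consecutive months (same places).
- Exit limit: 12 months (Table 4).
- All rows must be met (Table 4).
- Screening: assumed to fall in the planned recruitment period, 3 to 21 June 2024, with the program starting on 24 June (Section 2.5).

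**Strict reading: the whole spell lies inside the window**

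Let *t* be the months since the most recent exit. The homelessness that can lie inside the window is at most 12 - *t*, so the rule needs 12 - *t* ≥ 3, that is, *t* ≤ 9.

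- Repeated exits do not relax this, because the most recent exit cannot be earlier than the exit from the qualifying spell. A simulation of histories with several spells gave a maximum of 9.0 months.
- Window closed: (12 - 9)/12 = 3/12 = 25%.
- In dates: screening on 3 June 2024 needs a qualifying exit no earlier than 3 September 2023; screening on 21 June needs 21 September 2023.
- Example: homeless for 24 months, left 10 months ago, housed since. Only 12 - 10 = 2 months fall in the window, so this youth fails the three-in-twelve row and passes the exit row.

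**Lenient reading: a spell of at least three months that ended inside the window**

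The bound is *t* ≤ 12, and the simulated maximum was 12.0. The example youth is eligible, and nothing is lost from the first year.

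**Three months housed**

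The bullet and the Table 4 row both attach the three months to homelessness, and Table 4 has no row for time housed. This parse of the opening sentence is unlikely and is set aside.

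**What depends on the answer**

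| Element | Uses time since exit? |
|---|---|
| Sample size (Section 2.6) | No. It is pragmatic, with no formal calculation |
| Progression rule (Section 2.4) | No. It uses attendance below 50%, dropout above 30%, or overwhelmingly negative qualitative feedback |
| Pre/post comparison (Section 2.8.2) | No. It compares participants before and after the program |
| Named subgroups (Section 2.4) | No. The examples are gender, age, 2SLGBTQ+ identification and child welfare involvement, plus participation level |
| Recruitment and enrolment metrics (Table 2) | Only through who is counted as ineligible. No threshold is attached |

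**The case for a change.** The strongest case for a change is that the narrowing is real on the most natural reading of the bullet, has no stated reason, and sits beside a row whose 12-month limit it makes idle. Two screeners could decide the same youth differently. A coordinator who applies the words literally might see nothing to escalate, and the records described would not reveal the exclusion. Clarifying one line would cost almost nothing.

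Much of this stands as description: the bound is exact, the reason is missing, and the two readings do differ. It carries less weight as a case for change.

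- Targeting the first year does not promise that everyone in it is eligible. English comprehension, availability to attend and the similar-program exclusion also narrow the pool.
- The exit row is not useless under the strict reading, since it still screens out youth who have not left homelessness.
- The exit row and the looser wording in Section 2.6 both point a screener toward the wider window. A three-in-twelve no beside an exit-row yes is just the kind of doubt that Section 2.7 sends to the principal investigator.
- The screening script and log (Appendices F and G) are not in the documents. How the item is asked, and what the log would hide, is inferred from Section 2.7 alone.
- A tally of reasons for every criterion is a separate preference. Section 2.7 deliberately limits notes taken before consent to the attendance criterion, which is meant to inform the scale-up. A tally would also miss youth whom the community partners had already filtered out.

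**Conclusion.** The concern does not call for a change. On the strict reading the latest admissible exit is 9 months before screening, and 3 of the 12 months of the target window are closed. On the lenient reading none are. These are shares of the calendar; 25% would be a share of youth only if exits were spread evenly over the year, and the documents do not show that.

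On either reading the enrolled youth lie inside the stated first year, and the feasibility and acceptability results remain sound for those enrolled. The study recruits 30 youth purposively through three partner agencies and makes no claim to represent everyone in the year after exit. No calculation, test or progression threshold would come out differently because of the wording.

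What remains is a missing detail that the team can fill sensibly when screening, and a loosely attached clause in the opening sentence of Section 2.2 that the bullet and Table 4 already resolve. This conclusion assumes that the screening script does not impose some further limit, and that the report describes the participants as they were actually enrolled.
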